5. STUDY METHODS

a. General Study Design and Plan

This single-blind study uses a 3x2x2 factorial design. Upon confirmation of their name, patients are randomized to one of the 12 potential study arms immediately based on two stratification variables (race and sex). If the patient does not confirm their name via text message, the patients will not be randomized nor included in the study. Upon randomization, the participants immediately receive the assigned interventions via text message.

| 3x2x2 Study Design | Tobacco Use Message A | | Tobacco Use Message B | |
|------------------------|-----------------------|--------------|-----------------------|--------------|
| | Incentive | No Incentive | Incentive | No Incentive |
| Introductory Message A | Arm 1 | Arm 2 | Arm 3 | Arm 4 |
| Introductory Message B | Arm 5 | Arm 6 | Arm 7 | Arm 8 |
| Introductory Message C | Arm 9 | Arm 10 | Arm 11 | Arm 12 |

b. Inclusion-Exclusion Criteria and General Study Population

Inclusion Criteria: Based on available EMR data at the time of enrollment, patients will be eligible if they:

- meet age eligibility (50-80 years old) for LCS based on 2021 USPSTF guidelines
- have completed at least one primary care visit at Penn Medicine in 2020-2025
- have a mobile phone listed in their medical record
- confirm identify at the time of initial outreach via text message.

Exclusion Criteria: Based on available EHR data at the time of enrollment, patients will be ineligible if they:

- have a documented history of lung cancer
- have a documented history of completing LCS at Penn Medicine
- are listed as not wanting to be contacted or solicited for research
- do not otherwise meet inclusion criteria.

c. Randomization and Blinding

Participants will be randomized into one of 12 study arms at the time of name confirmation. Randomization will occur using the randomization module within the Way-to-Health platform and be stratified by sex (female vs non-female) and race (Black adult vs non-Black adult). Single blinding (statistician) will be used in this study. Participants are randomized in blocks of 24 (12 study arms).

d. Study Assessments

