7. GENERAL ANALYSIS CONSIDERATIONS

a. Timing of Analyses

The final analysis will be performed when at least 6,000 participants have randomized. The final analysis will be performed after all necessary cleaning and approval of statistician and after the finalization and approval of this SAP document.

b. Analysis Populations

i. Intention to Treat

All subjects who were randomized will be included in the intention to treat analysis. This will be the primary efficacy population for the purposes of the study.

ii. Per Protocol Population

All subjects who responded in any form (e.g., any text message response including but not limited to survey response) after receiving the intervention (i.e., after all interventions are delivered) will be included in the per protocol analysis. This will be the secondary efficacy population for the purposes of the study. This will exclude participants in the ITT that only confirmed their name and did not reply in any form after that.

c. Covariates and Subgroups

Covariates including baseline demographic (e.g., age, race, sex, ethnicity) and smoking history data (e.g., tobacco use status, lifetime smoking) will be extracted from the EHR. Variables used in randomization (sex and race) will be adjusted for in the primary analysis. We will assess baseline characteristics of each group by key covariates to assess any potential differences. Given persistent disparities in lung cancer by race and in LCS guidelines by race and sex, we will conduct exploratory subgroup analysis to assess potential treatment heterogeneity by race (Black adults vs Non-Black adults) and sex (female vs non-female). We do not hypothesize that our treatment will be different for each group, but given disparities, we conduct exploratory analysis to assess heterogeneity of treatment effects by race and sex.

d. Missing Data

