8. SUMMARY OF STUDY DATA

All continuous variables will be summarized using the following descriptive statistics: n (non-missing sample size), mean, standard deviation, median, maximum and minimum (as applicable). The frequency and percentages (based on the non-missing sample size) of observed levels will be reported for all categorical measures. In general, all data will be listed, sorted by study arm and subject, and when appropriate by outcome within subject. All summary tables will be structured with a column for each intervention and will be annotated with the total population size relevant to that table, including any missing observations.

a. Subject Disposition

We will identify participants to be included in ITT based on randomization assignment among all those contacted. Allocation assignment will be assessed using categorical variable assigned (defined as Arm 1- Arm 12) assigned at the time of randomization and stored within the survey platform. In order to identify patients who have completed the survey (primary outcome) or partially completed the survey (secondary outcome), we will use variables assessed from the survey platform (WaytoHealth) for each subject. The survey questions are coded based on the response (Yes =1; No=0) for each of the three questions. We will also conduct visual evaluation (i.e., review text responses) for any question where the natural language processing is less than 90% confident (as assigned by the survey platform). Below is a draft consort diagram that to be populated with number and proportion of participants in each cell.

b. Derived variables

The survey platform (WaytoHealth) uses natural language processing to interpret the text-based response
SAP version V.1 (November 25, 2023)

into a derived variable (Yes or No), using a pre-specified confidence threshold of 0.9. For any response, that does not reach this confidence threshold, the platform asks for clarification (i.e., “Please answer Yes or No”) from the participant. To ensure quality of the derived variables, we will review a random sample of questions that classified as yes or no (50 each). If we identify that more than 5% are misclassified by the platform, then we will review all responses. For any survey responses with a confidence threshold lower than 0.9, two members of the analytic team will independently review each response for interpretation and classification. If no agreement is reached, the survey response will be marked as unknown.

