9. EFFICACY ANALYSES

a. Primary Efficacy Analysis

All summary statistics will be produced in accordance with section 8, and all primary efficacy analyses will use the ITT population. All tests will be two-sided and use a Type I error of 0.05. First, we will test for a main effect of incentive versus no incentive using an independent proportions Z-test. If this main effect is significant, we will proceed to study the two messaging factors using only data from individuals randomized to the incentive condition with higher response rate. If the main effect of incentive is not significant, we will proceed with studying the two messaging factors using all data and assuming incentive level does not interact with messaging or have any other effect on the outcome. Next, using either half or all the data, we will model the binary indicator of complete survey response or non-complete survey response within 7 days using a logistic regression. The model will adjust for race and sex and will incorporate 5 indicators of treatment arm (3 introductory messaging levels x 2 tobacco use messaging levels – 1 reference group). We will compute the marginal response probability for each arm, averaging over the observed distribution of sex and race. Standard errors and 95% confidence intervals will be obtained for each marginal response probability using the delta method. If one of the confidence intervals has a lower limit that exceeds the upper limit of all the others, its corresponding set of factor levels will be used in the primary study, pending confirmation that exploratory analyses do not raise red flags about disparities in response rates. If a set of confidence intervals have lower limits that surpass the upper limits of the other intervals, the final choice of factor levels to use will be based on discussions amongst the study team and key stakeholder, taking into consideration the point estimate, confidence interval length, and exploratory data on disparities.

i. Secondary Analyses of Primary Efficacy Endpoint

We will conduct secondary analyses of the primary efficacy endpoint using the per protocol, instead of the ITT population, to assess if documented engagement after receipt of the full intervention affected efficacy.

ii. Analyses of Secondary Endpoints

We will conduct similar analysis outlined in Section 9a to assess the effect of the interventions on the secondary outcome, partial completion of the survey.

b. Exploratory Efficacy Analyses

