We will conduct exploratory efficacy analyses within each of the following pre-specified subgroups: 1) females vs non-females and 2) Black adults vs non-Black adults (using EHR data). We conduct primary and secondary efficacy analysis within each of these subgroups in accordance with section 9a and 9b above. The summary statistics will be produced in accordance with section 8. This subgroup analysis is justified because there are existing disparities in LCS guidelines in each of these groups and we aim to understand if our strategies may help to reduce or increase disparities before implementing them broadly.

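### The SAP asks whether message and incentive effects differ by race and sex, but plans only separate within-subgroup analyses and no between-group contrast with a confidence interval

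*SAP*

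**What the plan says.** **The question.** SAP section 7c (Covariates and Subgroups) states that "we conduct exploratory analysis to assess heterogeneity of treatment effects by race and sex". Section 9b (Exploratory Efficacy Analyses) adds the purpose: "we aim to understand if our strategies may help to reduce or increase disparities before implementing them broadly".

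**The method.** Section 9b then says: "We conduct primary and secondary efficacy analysis within each of these subgroups in accordance with section 9a and 9b above". It also calls for summary statistics as in section 8, where "All summary tables will be structured with a column for each intervention".

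**What 9a contains.** It opens with a Z-test of incentive against no incentive. If that is significant, the two messaging factors are studied "using only data from individuals randomized to the incentive condition with higher response rate". Otherwise: "If the main effect of incentive is not significant, we will proceed with studying the two messaging factors using all data". The logistic model that follows has race and sex as adjustment terms and five indicators for the six message combinations. It has no product of message or incentive with race or sex.

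**Where the result is used.** Section 9a adopts a clearly leading combination "pending confirmation that exploratory analyses do not raise red flags about disparities in response rates". When several combinations lead, data on disparities also enter the study team's discussion. No criterion for a red flag is given.

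**The concern.** Whether an effect differs between two groups is answered by estimating the difference between the effects, with its uncertainty. Section 9b instead gives one analysis per group and leaves the comparison to the reader. Two analyses can disagree on significance while the effects are identical, simply because each group is smaller than the whole and one may be smaller than the other.

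The two-branch structure of 9a adds a second difficulty. If the incentive test is re-run in each subgroup and is significant in only one, that group's message-arm rates refer to a single incentive condition, while the other group's average over both. The two sets of rates then do not estimate the same quantity.

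At stake is the adoption decision. The disparity check can hold back the leading combination, and no estimate of a between-group difference in effect is specified for it to use.

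**Working it through.** **The plan's own figure.** SAP section 6 says that 500 per arm separates two arms 5 points apart when the lower is at 3% to about 7%, and that 300 per arm does so only at 3% or lower. This reproduces as non-overlap of Wald intervals, p ± 1.96·√(p(1−p)/n). At n = 500, 3% gives 1.5 to 4.5 and 8% gives 5.6 to 10.4; the highest lower rate without overlap is 6.66%. At n = 300 it is 2.99%. The section 6 calculation concerns full-sample arms and says nothing about subgroups.

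**Inputs.** From the SAP: 6,000 randomized equally to 12 arms, so 3,000 per incentive condition; two-sided 0.05; response rates of 3% to 12%; no missing outcomes. Assumed, because the documents do not give them: base rate 7%, the same true incentive effect in both groups, and a smaller-group share of 20% to 50%.

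**Incentive test re-run per subgroup.** Power in a group with n per condition is about Φ(δ/√[(p₀(1−p₀)+p₁(1−p₁))/n] − 1.96). For 7% against 9% at a 20/80 split:

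- Smaller group, n = 3,000 × 0.2 = 600: √(0.147/600) = 0.01565; 0.02/0.01565 − 1.96 = −0.68; power 0.25.
- Larger group, n = 2,400: √(0.147/2,400) = 0.00783; 0.02/0.00783 − 1.96 = 0.60; power 0.72.
- Significant in exactly one: 0.247 × (1 − 0.724) + 0.724 × (1 − 0.247) = 0.61.

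At 50/50, power is 0.524 in each group and the chance is 2 × 0.524 × 0.476 = 0.50. With no effect it is 2 × 0.05 × 0.95 = 0.095. Simulation with the pooled Z-test agrees:

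| True incentive effect, equal in both groups | Test significant in exactly one group | Direct incentive-by-group contrast excludes zero |
|---|---|---|
| 0 | 9.5% | about 5% |
| 2 points | 50-61% | about 5% |
| 3 points | 27-54% | about 5% |
| 5 points | 1-16% | about 5% |

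**Effect on the message-arm rates.** With a true incentive effect of 2 points, the better condition lies 1 point above the average of the two. The larger group reaches that branch more often. A simple approximation to the resulting gap is 1 × (0.724 − 0.247) = 0.48 points at a 20% share and 1 × (0.666 − 0.346) = 0.32 at 30%. Simulation gives less, roughly 0.35 and 0.25, because a small group tends to reach significance when its rate in the better condition happens to run high. With equal groups the systematic gap is about zero. A common branch removes it.

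**Precision of a direct contrast.** The 95% half-width is 1.96·√(2p(1−p)(1/n₁+1/n₂)), with p = 0.07 and 2p(1−p) = 0.1302:

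- Incentive: n = 600 and 2,400 gives 3.2 points; 1,500 and 1,500 gives 2.6.
- One message combination against the reference, all data (1,000 per combination): 200 and 800 gives 5.6; 500 and 500 gives 4.5.
- The same on half the data (500 per combination): 100 and 400 gives 7.9; 250 and 250 gives 6.3.

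**The case against.** **The analysis is exploratory, and no heterogeneity is hypothesized.** True, and the point is modest for that reason. But 9a gives the result a role in the decision, so the label does not remove the need for a defined estimate.

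**More is planned than the subgroup sentence suggests.** Section 9b's reference to section 8 may yield response rates by subgroup and arm, and the protocol's Statistical Analysis section plans descriptive response by demographics. The 9a model's race and sex terms reflect overall differences in response between groups. Female and non-female, and Black and non-Black, are disjoint groups, so where both use the same branch a difference with an interval could be worked out from the planned output. All of this stands. The tables are descriptive, however, the main-effect terms do not address differences in effect, and the derived contrast is not specified and does not compare like with like when the branches differ.

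**A reader might infer that the SAP ignores the incentive test in subgroups.** It does not: 9b imports 9a, and 9a begins with that test, so a re-run is the plain reading. What is missing is an explicit statement, and what to do when the groups differ.

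**A reader might infer that 50-61% is a rate of wrong vetoes.** The documents do not say that significance will be compared between subgroups, and a red flag has no criterion, so no such rate can be computed.

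**A reader might infer that a common branch would reduce chance gaps between groups.** At the message-arm level, which is what 9a reports, it does not. With a 2-point incentive effect, the mean absolute gap is 1.9-2.2 points as planned and 1.9-2.4 with a common branch; gaps of 2 points or more occur in 40-47% and 42-51%. The common branch is slightly noisier because the full-sample test is significant in 82% of trials, which puts both groups on half the data.

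**Conclusion.** The concern holds in a limited form. The SAP asks a between-group question, attaches an adoption decision to it, and specifies no between-group contrast with a confidence interval. Separate subgroup results are the only inferential output available to the disparity check, and they are a poor guide to heterogeneity: with identical effects, the incentive test would disagree between groups in about half or more of trials at 2 points, against about 5% for a direct contrast. At 5 points the disagreement falls to 1-16%.

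The change of estimand when branches differ is real but small: roughly 0.25-0.35 points at a 2-point effect with a 20-30% share, and about none with equal groups. It arises only if the incentive test is re-run per subgroup; if the full-sample branch is carried over, only the missing contrast remains.

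The figures rest on the assumed 7% base rate, the assumed shares and equal true effects. The self-reference to 9b inside 9b probably means 9a.i and 9a.ii; it is an editorial slip with no analytic consequence.

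**What to change.** In section 9b:

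- Estimate incentive-by-race and incentive-by-sex contrasts on all ITT participants.
- State that the branch chosen in the full ITT analysis applies to every subgroup, so that message-arm rates refer to the same incentive condition(s).
- On that common data set, add message-arm-by-race and message-arm-by-sex terms to the 9a model.
- Report between-group differences in response-rate differences with 95% confidence intervals, beside response rates by group and arm.
- Correct the self-reference.

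In section 9a, base the disparity check on these estimates and intervals, not on which subgroup passed the incentive test or the interval-separation rule.

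The cost is SAP wording and a few model terms on factors already used to stratify randomization; no new data are needed. The downside is precision: half-widths of about 2.6-3.2 points for incentive and 4.5-8 for message contrasts, on a 7% base rate. The check will remain exploratory and often inconclusive. The common branch secures comparability only; it does not reduce noise in the arm-level gaps.

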10. SUMMARY OF CHANGES TO THE PROTOCOL AND/OR SAP

This statistical plan outlines analysis for the experimental trial, which is part of a larger, multiphase study that will be informed by this phase of study.

